6.3 Modified Intent-to-Treat (mITT) Population

The mITT population includes all subjects randomized that meet the following criteria:

- Received at least one dose of study medication.
- Correctly completed the Daily Pain and Sleep Interference Diary at the 3-month follow-up, i.e., by completing a minimum of 5 of 7 days of diary entries within 14 days prior to the Day 90 visit.
- For the mITT population, entries in the Daily Pain and Sleep Interference Diary will be considered fully valid if made anytime during the 24 hour period specified in the date entry.
- Satisfies Inclusion/Exclusion criteria

Subjects will be grouped based on the randomly assigned treatment, not the actual treatment administered. The mITT population will be used in the sensitivity analyses for the primary and secondary efficacy endpoints.

6.4 Per Protocol (PP) Populations

Three PP populations are defined. All PP population should be absent of any major protocol deviations.

The Per Protocol Medication population is a subset of the mITT and corresponds to the mITT population defined in protocol version H. It includes all mITT subjects who meet the following criterion:

• Have not used the protocol specified prohibited concomitant medications, such as COX-2 inhibitor drug(s) or non-specific COX-1/COX-2 inhibiting drugs which may interfere with VM202 or pain medication usage which may intensify the effect of VM202/placebo on pain, for more than 14 cumulative days during the entire study. The use and effect of protocol specified prohibited concomitant medications will be determined by the Clinical Data Review Committee (CDRC) in a blinded fashion prior to analyses.

The Per Protocol Dosing population is a further subset of the mITT and corresponds to the PP population defined in protocol version H. It includes all mITT subjects who meet the following criterion:

- Subject received all injections based on the randomized treatments.
- Additional criteria, if any, established before unblinding the randomization code by the CDRC that is masked to the treatment information of each study subject.

The Per Protocol Diary population is a subset of the mITT and includes all mITT subjects whose Daily Pain and Sleep Interference Diary at the 3-month follow-up is completed for a minimum of 5 of 7 days within 14 days prior to the Day 90 visit.

All three PP populations will be used in the sensitivity analyses for the primary efficacy endpoints. The PP Medication and PP Dosing populations will also be used in sensitivity analyses of the secondary efficacy endpoints.

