8.4. Efficacy Endpoints Analyses

8.4.1. Primary and Secondary Efficacy Endpoints

Subjects will be asked to assess the level of pain they feel by selecting a score from 0 (No Pain) to 10 (Worst Possible Pain) in the Daily Pain and Sleep Interference Diary for 7 days at screening (the baseline for the pain score), 3-month, 6-month, and 9-month visits. The Daily Pain and Sleep Interference Diary must be completed within the 14 days prior to each specified visit. The average of the available pain scores from the Daily Pain and Sleep Interference Diary will be calculated for each subject at each visit and will be rounded to the first decimal point.

The primary efficacy endpoints are the change in average 24-hour pain score as determined by the Daily Pain and Sleep Interference Diary between baseline and the 3-month follow-up and outcome of a pain score change of \leq -50% at 3 months. The change and the percent change in pain will be calculated for each subject as follows:

Change = 3-month Pain Score – Baseline Pain Score

% Change = Change \div Baseline Pain Score \times 100%.

Since higher scores indicate worse pain, a negative value of change means an improvement, and a positive value of change means deterioration. Subjects with a percent change of \leq -50% (i.e., reduction of at least 50%) will be classified as a responder at 3 months. The means of the change in the average 24-hour pain score at 3 months and the percentage of subjects with a change in the average 24-hour pain score of \leq -50% will be compared between the treatment groups (VM202 and placebo) at 3 months.

The key secondary efficacy endpoints are the change in the average 24-hour pain score from baseline to the 6-month follow-up, and the outcome of reduction in average 24-hour pain score of at least 50% at 6 months. The means of the change in the average 24-hour pain score at 6 months and the percentage of subjects with a change in the average

24-hour pain score of \leq -50% will be compared between the treatment groups (VM202 and placebo) at 6 months.

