8.4.4. Sensitivity Analysis of the Primary and Secondary Efficacy Endpoints

To further evaluate the robustness of the primary and secondary efficacy outcomes, the Repeated Measures Model analyses described in Section 8.4.2 will be performed on the imputed data sets described in Section 7.7.1.

Additionally, two sets of the Repeated Measures Model analyses will be performed without missing value imputation. For the first set, analysis will be conducted in the ITT, mITT, and PP populations using all available average 24-hour pain score data (i.e., observed cases). For the second set conducted in the ITT and mITT populations, any individual pain scores influenced by the protocol-prohibited concomitant medications, as described in Section 6.4, will also be excluded.

The point estimates for the least-squares mean of the treatment difference (VM202 – Placebo) at 3 and 6 months, and the corresponding 95% confidence intervals and p-values, will be summarized.

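### Per-protocol sets used to check the Day 90 endpoints are selected partly on events after the Day 90 diary; separately, the unmasked DSMB may advise on deviations that affect membership

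*SAP*

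**What the plan says.** The primary endpoints rest on the 3-month diary, which "must be completed within the 14 days prior to each specified visit" (SAP 8.4.1). Injections are given on Days 0, 14, 90 and 104 (SAP 3), and Protocol 3.4.13 places the diary ahead of the Day 90 visit at which the third set is given.

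SAP 6.4 then defines the PP sets:

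- **All three:** "All PP population should be absent of any major protocol deviations". No time limit is attached, and Protocol 6.2.4 adds none.
- **PP Dosing:** "Subject received all injections based on the randomized treatments".
- **PP Medication:** no use of protocol-specified prohibited drugs "for more than 14 cumulative days during the entire study".
- **PP Diary:** at least 5 of 7 diary days at 3 months.

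On their use, SAP 6.4 says: "All three PP populations will be used in the sensitivity analyses for the primary efficacy endpoints". PP Medication and PP Dosing also serve the secondary (6-month) endpoints.

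The protocol's restriction periods differ by drug. Opioids and the other therapies on the washout list are barred to the 9-month visit (Protocol 3.4.5.2 and the washout appendix). For COX inhibitors and steroids, Protocol 3.4.5.1 describes a ban during the study and, in the next sentence, one that runs to the Day 180 visit.

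On masking, SAP 7.3 unmasks the randomization code to the DSMB, and SAP 7.5 allows the DSMB to be asked for guidance on deviations that could change PP membership. Additional PP Dosing criteria, by contrast, are to be "established before unblinding the randomization code by the CDRC that is masked to the treatment information of each study subject".

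**The concern.** A subject who follows the protocol fully to Day 90 and then declines the third injection leaves the PP Dosing analysis of the 3-month endpoint, although nothing about that subject's 3-month exposure or outcome has changed. Poor pain relief is a plausible reason to decline further injections or to take a prohibited analgesic. Membership would then depend on the outcome that the analysis is meant to check, and agreement or disagreement with the ITT result would be hard to read.

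PP Diary is exposed only through the untimed deviations rule. For the 6-month endpoints all four injections come before the diary, so the PP Dosing injection rule raises no timing problem there. PP Medication still counts use after Day 180 of drugs restricted to 9 months, and the deviations rule remains open-ended.

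The DSMB sentence raises a different question: whether a body that knows the treatment codes should have any voice in deciding which deviations remove a subject.

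**Working it through.** **Timing, side by side**

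| Rule | Reaches past the 3-month diary? | Reaches past the 6-month diary? |
|---|---|---|
| PP Dosing, all injections | Yes: Day 90 and Day 104, two of four visits | No |
| PP Medication, entire study | Yes: about 180 of 270 days | Yes, for drugs restricted to 9 months |
| No major deviations (all three sets) | Yes, untimed | Yes, untimed |

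**The plan's own figure.** With SD 3.0, 286 VM202 and 143 placebo subjects and a difference of 1.0 (SAP 5), SE = 3 x sqrt(1/286 + 1/143) = 0.307. The two-sided 5% t-test has 90.1% power, which reproduces the stated 90%.

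**Model for the selection.** The documents give no PP exclusion rates, so these are assumed. Day 90 change is taken as normal with SD 3.0. The placebo mean is -1.7 (Phase II ITT, Month 3) and the VM202 mean is -2.7 (the plan's difference of -1.0). A subject whose change is above a cut-off c is later excluded with probability a, and any other subject with probability b. Let P be the proportion at or below c, and let L and U be the mean changes below and above it:

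retained mean = [P(1-b)L + (1-P)(1-a)U] / [P(1-b) + (1-P)(1-a)]

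This compares simple means, not the repeated-measures model.

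**Same rule in both arms, a = 25%, b = 5%, c = -1**

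- VM202: P = 0.7145, L = -4.127, U = 0.871. Proportion retained = 0.6788 + 0.2141 = 0.8929; retained mean = -2.928.
- Placebo: P = 0.5922, L = -3.667, U = 1.156. Proportion retained = 0.5626 + 0.3058 = 0.8684; retained mean = -1.968.
- Difference -0.960, a shift of 0.13 SE (0.040/0.307). About 31 VM202 and 19 placebo subjects are lost.

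| Cut-off c | 0 | -1 | -2 | -3 | -4 |
|---|---|---|---|---|---|
| Difference (truth -1.0) | -0.95 | -0.96 | -0.99 | -1.02 | -1.04 |

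At c = -1, rates of 15/3% and 40/5% give -0.98 and -0.91; 40/5% at c = -4 gives -1.07. With no true effect and equal SDs the two arms are identical and the shift is zero. If the SDs differ as in Phase II ITT (2.47 and 1.72) and both means are -1.7, the 25/5% rule at c = -1 gives -0.07.

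**Exclusion that differs by arm, c = -1, others 5%**

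| Exclusion above c, VM202 v placebo | No true effect | Truth -1.0 |
|---|---|---|
| 25% v 15% | -1.968 - (-1.828) = -0.14 | -2.928 - (-1.828) = -1.10 |
| 15% v 25% | +0.14 | -2.811 - (-1.968) = -0.84 |

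With no true effect, nominal 5% rejection in that set becomes about 7.2% at 25% v 15%.

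**Responder endpoint, same exclusion rule, c = -1.** Take responders as the best 35% and 18% of each arm's change distribution (the planning rates). Their thresholds, -3.86 and -4.45, lie below -1, so all responders face rate b: p' = p(1-b)/(proportion retained).

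- 25/5% in both arms: 0.35 x 0.95/0.8929 = 0.372 and 0.18 x 0.95/0.8684 = 0.197, odds ratio 2.42 against a true 2.45. Rates of 15/3% and 40/5% give 2.43 and 2.39.
- 25% v 15%: odds ratio 1.06 with no effect (18% in both arms), and 2.56 against a true 2.45.

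**DSMB.** No arithmetic applies. SAP 7.3 withholds unmasked summaries from the CDRC but does not expressly cover advice. SAP 6.4 gives the masked CDRC the medication review and any added criteria. The visible text does not say who decides which deviations are major.

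**The case against.** The strongest reply is that nothing decisive depends on these sets. Primary inference is in the ITT population. Of the mITT set, SAP 6.3 says: "The mITT population will be used in the sensitivity analyses for the primary and secondary efficacy endpoints". Its own criteria do not reach past the 3-month diary. The imputation analyses in SAP 7.7 do not use PP membership. SAP 8.4.4 already handles medication at the level of the score: "For the second set conducted in the ITT and mITT populations, any individual pain scores influenced by the protocol-prohibited concomitant medications" are dropped. All of this stands and limits the severity.

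It can also be said that one model covers 3, 6 and 9 months, so one whole-study adherent set is a coherent choice. That is fair for a whole-study question, but SAP 6.4 assigns the sets to the 3-month endpoints, where later adherence is not part of the exposure. The exclusion rates above are assumed, and a marked difference between arms is less likely in a double-blind trial. That stands too.

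On the DSMB, the sentence is permissive and advisory, SAP 7 sends questionable situations to the CDRC for final review, and the Charter is not visible. A reader might infer that unmasked people decide PP membership. The documents do not say so. They leave open a route for unmasked advice.

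**Conclusion.** The concern holds as a minor-to-moderate defect in supportive analyses. All three PP sets, as applied to the 3-month endpoints, have at least one membership rule that reaches past the 3-month diary. The ITT primary analysis, its type I error, mITT, the imputation analyses and the ITT/mITT runs without medication-influenced scores are untouched.

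Under the assumed rates, a common 25/5% rule moves a true -1.0 by about 0.05 points or less. Exclusion of 25% against 15% by arm moves it by 0.10 to 0.16, and moves a null difference by 0.14. The responder odds ratio moves little: 2.39 to 2.43 under a common rule, 2.56 at 25% v 15%. These figures rest on a normal model with the plan's SD, a sharp cut-off and assumed rates.

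Two stronger inferences are tempting and unsupported. One is that the rules systematically favour VM202: nothing in the documents shows exclusion differing by arm. The other is that a rule common to both arms can only dilute the effect: with equal SDs the shift is toward zero at cut-offs of 0 to -2 but away from it at -3 and -4.

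The DSMB point is separate, and its effect cannot be quantified.

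**What to change.** Define the PP sets per endpoint in SAP 6.4:

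- **3-month endpoints:** PP Dosing uses the Day 0 and Day 14 injections. PP Medication and major deviations count only to the end of the 3-month diary.
- **6-month endpoints:** PP Dosing uses all four injections. Medication and deviations count to the end of the 6-month diary.
- State how the 14-day limit applies to each window.
- Reconcile the SAP's whole-study medication count with the protocol's drug-specific restriction periods, including the two statements in Protocol 3.4.5.1.
- State which PP Dosing version the 9-month Tylenol summary (SAP 8.6.2) uses.

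Separately, delete the sentence in SAP 7.5 on DSMB guidance about PP deviations. State that the masked CDRC finalises PP membership, including which deviations are major, before unblinding.

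The cost is SAP wording, extra population flags, and separate continuous and categorical PP model runs for each endpoint, because one model now yields both the 3- and 6-month results (SAP 8.4.3). No new data are needed.

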6.5 Subgroup Analysis Subsets

The subgroup analyses will be exploratory in nature and will be conducted in the ITT population. The primary and secondary efficacy endpoints will be evaluated based on the categories of the covariates described in Section 4.6 as well as the randomization stratification factor. Age will also be categorized as <65 years and \geq 65 years. These subgroups will be re-examined and may be re-categorized or eliminated due to small sample size (if there are < 10% of subjects within each subgroup) before unblinding for analysis. For example, if < 10% of overall subjects are \geq 65 years, then analyses for this subgroup will not be performed. Descriptive summaries for the primary and secondary efficacy endpoints will also be provided for each study center regardless of the sample size per center, and similarly for the different protocol versions.

Nerve conduction velocity (NCV) analysis will be performed on an NCV sub-population. The NCV sub-population will include all randomized subjects that have at least one postbaseline NCV assessment.

The treatment by subgroup interaction will be examined and tested as described in Section 8.4.5. Data Handling

7. GENERAL PRINCIPLES OF DATA HANDLING

Data screening will be conducted in a blinded fashion periodically during the conduct of the study. The objective of the data screening is to assess the quantity, quality, and statistical characteristics of the data relative to the requirements of the planned analyses. The designated Contract Research Organization (CRO) will be responsible for data cleaning and dictionary coding of AEs, medical history, and medications. Any

questionable values or situations will be reported to the CDRC for final review and confirmation.

7.1. Baseline Definition

Unless specified otherwise, the baseline value for each variable is the value recorded at the last visit on or before start of dosing.

For the pain and sleep interference scores from the Daily Pain and Sleep Interference Diary, the baseline value is the average 24-hour pain score and average sleep interference score from the diary collected prior to Day 0.

It should be noted that, for eligibility, the average 24-hour pain score of the Daily Pain and Sleep Interference Diary completed after medication wash-out, if applicable, should be ≥ 4 with a standard deviation ≤ 2 at Screening and within the 14 days prior to Day 0. For the average 24-hour pain score or the sleep interference score calculation, at least five (5) days need to have the available scores.

7.2. Visit Windows

Data at each scheduled follow-up visit will be analyzed according to the nominal visit identified on the data record.

In case of multiple different visits with the same nominal visit designation, the visit with the visit date closest to the target days of each protocol specified visit schedule (Table 3) will be used for the efficacy analyses. For visits with the same distance to the target days, the later nominal visit record will be used. Data from the other visits (if any) will be provided in data listings only.

					100.00	1.1.013				
VISIT	1 st INJECTION	2 ND INJECTION	DAY 21	Month 2	3 RD INJECTION	4 ^{тн} Injection	DAY 111	MONTH 5	MONTH 6	Month 9
TARGET DAY	0	14	21	60	90	104	111	150	180	270

TABLE 3.	Target	Day

7.3. Unmasking of Randomization Codes

Following database lock, the randomization code will be unmasked to the project team.

The randomization code will be unmasked to the Data Safety Monitoring Board (DSMB; Section 7.6) members and the team that will prepare the unmasking summary tables for the DSMB meetings. However, in order to prevent bias, the unmasking detailed data summaries will not be shared with the sponsor management team, the CDRC, or the team that is monitoring the clinical data collection. The subject and study personnel, including core lab, principal investigator, co-investigators, study coordinators, study monitors and study director will remain blinded to individual data and group results until all data has been entered into the database and the database is locked.

7.4. Multiplicity Adjustment

There is no adjustment of the type 1 error rate based on multiplicity. A step-down approach will be used that controls for the potential inflation of the type 1 error rate.

The analyses of the primary efficacy endpoints will be conducted hierarchically based on the order of the two primary efficacy endpoints. Similarly, the analyses of the two secondary efficacy endpoints will be conducted hierarchically based on the corresponding order for the two secondary efficacy endpoints. The secondary efficacy endpoints will be tested only when the null hypotheses of both the primary efficacy endpoints are rejected at a significance level of 0.05^2 .

The significance level for each exploratory efficacy endpoint will be 0.05.

All statistical testing will be 2-sided.

7.5. Data Safety Monitoring Board

An independent DSMB will periodically review a limited set of unblinded tables and/or listings, including all reported AEs. The objectives of the DSMB meetings are to review the safety outcomes of the study and provide guidance to study sponsor regarding the safety of the VM202. The data analyses for the DSMB meetings will be directly

² Alex Dmitrienko and Ralph D'Agostino, Sr., "Traditional multiplicity adjustment methods in clinical trials." Statistics in Medicine, 2013; 32(29):5172-218.

provided to the DSMB members and no data will be released to the study sponsor and blinded designees. There will be no adjustment for multiple testing due to the DSMB data review. The DSMB may be asked to review and provide guidance regarding protocol deviations that may affect the determination of the PP populations. Further details of DSMB responsibilities are included in the DSMB Charter.

7.6. Handling of Missing and Incomplete Data

Subjects may have missing specific data points for a variety of reasons. In general, data may be missing due to a subject's early withdrawal from study, a missed visit, or a clinical parameter not measured at a particular point in time. The general procedures outlined below describe how missing data will be addressed in the analyses.

7.7. Missing Average 24-hour Pain Scores at 3, 6, or 9 Months

The Daily Pain and Sleep Interference Diary is to be completed within 14 days of the 3-, 6- and 9-month visits. The average 24-hour pain score for a visit will be considered as missing if fewer than 5 of 7 days of Daily Pain and Sleep Interference Diary entries are provided. Sensitivity analyses for the mean change in the average 24-hour pain score will include the following imputation approaches for missing values at 3-months, 6-months, or 9-months. It is important to note that over-stratification may result when the total list of pre-specified factors are considered. Under this scenario, the least represented factor will be removed and the imputation will be re-run. This process will be followed until the imputed dataset is complete.

- Multiple imputation: Each missing pain score will be imputed ten times to generate ten imputed complete data sets based on the Markov Chain Monte Carlo (MCMC) method with baseline pain score, 3-month, 6-month, 9 month pain score, and categorical covariates of baseline use of gabapentin and/or pregabalin, baseline HbA1c, gender, and age. The imputed score will be rounded to the first decimal point. The results of the ten tests from the continuous Repeated Measures Model (Section 8.4.2) using these data will be combined.
- Mean of the other group $(MOTH)^3$ as follows:
 - 1. For a subject with a missing 3-month, 6-month, or 9-month average 24-hour pain score, identify the subject's following baseline characteristics:
 - Study treatment group
 - Baseline use of gabapentin and/or pregabalin.

³ Unnebrink K and Windeler J, "Intention-to-treat methods for dealing with missing values in clinical trials of progressive deteriorating diseases," Statistics in Medicine, 2001;20: 3931-3946.

- Baseline average 24-hour pain score (< median or \geq median)
- HbA1c (< median or \geq median)
- Gender (male or female)
- Age (<65 years and \geq 65 years).
- 2. The missing 3-month, 6-month, or 9-month average 24-hour pain score will be imputed by using the mean average 24-hour pain score obtained at the same time point of those subjects in the other treatment group who match the subject's baseline characteristics. For example, for the missing pain scores of the VM202 subjects, the mean pain scores of the placebo subjects within the same covariate groups will be used to impute the missing pain scores.
- 3. The baseline characteristics will be re-examined for appropriateness and may be re-categorized (due to small sample size) before unblinding the study.
- 4. The imputed score will be rounded to the first decimal point. The imputed scores will be included in the continuous Repeated Measures Model (Section 8.4.2) analysis.

Sensitivity analyses for the percentage of subjects with a reduction in the average 24-hour pain score of at least 50% will include the following imputation approaches for missing values at 3, 6, or 9 months.

- Imputed average 24-hour pain scores at 3, 6, or 9 months from the multiplyimputed pain score datasets described above. The results of the ten tests from the categorical Repeated Measures Model (Section 8.4.2) will be combined.
- Missing pain score will be imputed from the MOTH-imputed dataset described above and the categorical Repeated Measures Model (Section 8.4.2) will be used for the data analyses.
- Multiple imputation for the missing responder outcomes, 1 (Yes) or 0 (No), by fully conditional specification logistic regression method: each missing responder outcome will be imputed ten times to generate ten imputed complete data sets using a logistic regression model with baseline use of gabapentin and/or pregabalin, and categorical baseline HbA1c, gender, and age as covariates. The results of the ten tests from the categorical Repeated Measures Model (Section 8.4.2) will be combined.

Steps to generate the MMRM analysis are presented below; different options will be used depending on the exact model being run:

Run PROC MI using output dataset ("outmi") containing the original and imputed values, add "by imputation" to the SAS code and "solution" as an option on the MIXED model statement. The resulting file is available via ODS output: solutionf=mixparms;"

Run the following PROC MIANALYZE code: PROC MIANALYZE parms(classfull)=mixparms; class trtp avisitn basemed; modeleffects intercept trtp avisitn trtp*avisitn basemed; run;

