5. SAMPLE SIZE CALCULATION

Table 2 provides the summary statistics for the corresponding efficacy endpoints based on change in the average pain score for the low dose and placebo groups from the intent-to-treat population and efficacy groups in the Phase II study (Protocol VMDN-002, injections at Day 0 and Day 14 only).

	ľ	T	EFFICACY				
	VM202	PLACEBO	VM202	Placebo			
		Mean ((SD)				
Month 3	-2.89 (2.47)	-1.70 (1.72)	-3.03 (2.53)	-1.53 (1.76)			
Month 6	-2.58 (2.18)	-1.63 (1.75)	-2.78 (2.23)	-1.59 (1.89)			
	Percentage of Subjects with $a \ge 50\%$ Reduction						
Month 3	45.9%	23.8%	48.4%	17.6%			
Month 6	34.3%	15.0%	38.7%	17.6%			

TABLE 2. Mean and Standard Deviation of Pain Score Changes fromBaseline and the Percentage of Subjects with at Least a 50% Reduction;Low Dose versus Placebo Group in Phase II Study

The sample size for the primary efficacy endpoints was calculated based on the following assumptions:

- Based on the Phase II findings, it is assumed that the standard deviation of the pain score change from baseline will be 3.0. The true percentage of subjects with a pain reduction of ≥ 50% is assumed to be 35% and 18% for the VM202 group and placebo group, respectively.
- The statistical power is 90% for a detectable mean difference of -1.0 (i.e., mean pain reduction for the VM202 group is higher than that for the Placebo group) for Statistical Hypotheses (I) in Section 4.1 using a t-test. The statistical power is also 90% for Statistical Hypotheses (II) in Section 4.1 provided the assumptions of $p_t = 35\%$ and $p_c = 18\%$ using a chi-square test.
- The two-sided significance level is 0.05. Since a formal statistical conclusion for the second primary efficacy endpoint will not be made unless the null hypothesis of the first primary efficacy endpoint is rejected, no adjustment on the significance level is performed.
- The randomization ratio for the VM202 group and the placebo group is 2:1.

Based on the assumptions above, the sample sizes calculated for the VM202 group and placebo group are 286 and 143 subjects, respectively, for Statistical Hypotheses (I); those for Statistical Hypotheses (II) are 212 VM202 subjects and 106 placebo subjects.

Therefore, 286 VM202 subjects and 143 placebo subjects are needed with data at the 3-month follow-up for the primary data analyses. With a dropout rate of 10%, at least 477 subjects should be randomized in order to have 318 VM202 subjects and 159 placebo subjects.

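### The responder version of the mean-of-the-other-group (MOTH) sensitivity analysis cuts an imputed mean at 50%, so at the planned and Phase II rates missing subjects respond less often than the arm they borrow from

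*SAP*

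**What the plan says.** SAP 7.7 lists MOTH among the sensitivity analyses for missing Month 3, 6 and 9 scores. The rule is that a missing value "will be imputed by using the mean average 24-hour pain score obtained at the same time point of those subjects in the other treatment group". Only donors with the same baseline characteristics as the subject are used. The matching factors are gabapentin/pregabalin use, baseline pain (median split), HbA1c (median split), gender and age (under 65, or 65 and over). The imputed score is rounded to one decimal.

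If the full list of factors stratifies too finely, "the least represented factor will be removed and the imputation will be re-run", and this repeats until the dataset is complete. A separate step allows the baseline characteristics to be regrouped before unblinding when samples are small.

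For the responder endpoint the instruction is "Missing pain score will be imputed from the MOTH-imputed dataset described above", followed by the categorical repeated measures model. SAP 8.4.1 and 8.4.2 define a responder by a fall of at least 50% from the subject's own baseline. The SAP does not write out the cut for MOTH-imputed scores, but it gives no other route from the score to a yes/no outcome.

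Section 7.7 has two other imputation analyses for this endpoint: multiple imputation of the score, and logistic multiple imputation of the 0/1 outcome.

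**The concern.** MOTH is meant to ask what happens if missing VM202 subjects fared like placebo subjects, and the reverse. For a difference in means, inserting the other arm's mean does that. Response is different, because it depends on how many individual scores fall below half of baseline, and so on the spread of scores as well as their mean. A single cell mean keeps the mean and discards the spread. Whether an imputed subject then counts as a responder depends on where their own baseline sits within a median-split cell, and on noise in small cells. The proportion of donors who responded does not enter.

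At stake is the interpretation of the only listed analysis that gives missing subjects the other arm's experience on the second primary endpoint, which gates the secondary endpoints (SAP 7.4). The same applies to its Month 6 counterpart.

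**Working it through.** **1. The plan's own figures (SAP 5).** Inputs: "The two-sided significance level is 0.05"; "The statistical power is 90% for a detectable mean difference of -1.0"; "it is assumed that the standard deviation of the pain score change from baseline will be 3.0"; responder rates "assumed to be 35% and 18% for the VM202 group and placebo group, respectively"; "The randomization ratio for the VM202 group and the placebo group is 2:1".

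- Means: n(placebo) = (1.960 + 1.282)² × 3.0² × (1 + 1/2) / 1.0² = 141.9, or 142. With the t distribution, power is 0.8990 at 142 and 0.9010 at 143. This gives 286/143, as stated.
- Proportions: the pooled rate is (2 × 0.35 + 0.18)/3 = 0.2933. n(placebo) = [1.960 √(1.5 × 0.2933 × 0.7067) + 1.282 √(0.35 × 0.65/2 + 0.18 × 0.82)]² / 0.17² = 105.7. This gives 212/106, as stated.
- Dropout: 429/0.9 = 476.7, so 477 (318/159). About 32 VM202 and 16 placebo subjects would be missing.

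**2. When does an imputed mean count as a response?** For a subject whose baseline equals the cell's mean baseline B, a mean change d gives a reduction of |d|/B. It reaches 50% only if B ≤ 2|d|. With the Phase II ITT Month 3 figures in SAP Table 2:

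- Placebo, d = −1.70: break-even B = 3.40, below the entry minimum of 4. At B = 5 the reduction is 34%, and at B = 8 it is 21%. Yet 23.8% of placebo subjects responded.
- VM202, d = −2.89: break-even B = 5.78. At B = 5 the reduction is 58%, and at B = 8 it is 36%. Yet 45.9% responded.

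**3. Benchmarks at planning rates, 10% missing.** The observed difference is 35 − 18 = 17.0 points.

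- Missing subjects respond at the other arm's rate: (0.9 × 0.35 + 0.1 × 0.18) − (0.9 × 0.18 + 0.1 × 0.35) = 33.3% − 19.7% = 13.6 points.
- No missing subject responds: 0.9 × 17.0 = 15.3 points.

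**4. Simulation of the SAP rule.** 318/159 subjects, 10% missing completely at random, scores rounded to 0.1, then the 50% cut. Matching used either all five factors (2⁵ = 32 cells, so about 143/32 = 4.5 placebo donors per cell if evenly spread) or the baseline median alone. Assumptions not in the documents: baseline mean parameter 5.5 to 7.5 with SD 1.4, truncated to 4–10, and independent 50/50 matching factors. SDs of change were 3.0/3.0 or 2.47/1.72. Mean changes were set to give the stated responder rates.

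| Rates (VM202/placebo) | Imputed responders, VM202 missing | Imputed responders, placebo missing | Difference, SAP rule | Difference, rate-based |
|---|---|---|---|---|
| Planning 35%/18% | 0–8% (donors 18%) | 0–18% (donors 35%) | 14.1–15.4 | 13.4–13.7 |
| Phase II ITT 45.9%/23.8% | 0–13% (donors 23.8%) | 15–37% (donors 45.9%) | 16.4–18.1 | 17.4–17.6 |

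Compared setting by setting, the SAP rule exceeds the rate-based version by 0.7 to 1.7 points at planning rates. At Phase II rates the gap runs from −1.1 to +0.7. With all five factors the gaps are smaller: +0.7 to +1.1, and −0.3 to +0.1.

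A separate simulation over 32 cells with 10–20% missing gave 4–14% imputed responders in VM202 (donors 14–25%) and 9–45% in placebo (donors 30–50%). The imputed share was below the donor rate in every setting. The difference was within about 1 point of the rate-based version at 10% missing and about 2 points at 20%.

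For a limiting case at 20% missing and planning rates, suppose no imputed subject responds. The difference is then 0.8 × 17.0 = 13.6 points, against (0.8 × 0.35 + 0.2 × 0.18) − (0.8 × 0.18 + 0.2 × 0.35) = 10.2 points, a gap of 3.4.

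**5. Does the imputed share follow the donor rate?** It does, but not in proportion. With SD 2.5, a donor rate of 20% gives 0–2% imputed responders, 35% gives 0–15%, 50% gives 41–46%, 60% gives 65–74% and 70% gives 85–99%.

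**6. Empty cells.** With 50/50 factors and no regrouping, at least one missing subject had no donor in 15–24% of simulated trials at 10% missing and in 30–48% at 20%. All five factors are recorded for every subject, so the least represented one is not identified. Whether a donor cell is empty can be seen only with treatment codes.

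**The case against.** The strongest reply is that MOTH does what the SAP defines: it imputes the other group's mean score. The SAP nowhere promises that the responder version will reproduce the other arm's response rate. That stands. A reader might infer that the method is misnamed, but on the score scale the name is accurate.

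A reader might also infer that imputed subjects become non-responders whatever the donor rate, or that this is non-responder imputation under another label. Step 5 rules out the first: above a donor rate of about 50–55%, most imputed subjects become responders. The second fits only some settings. At planning rates with baseline-only matching, the SAP rule gives 14.8–15.4 points, against 15.1–15.4 if nobody imputed responds. At Phase II rates with all five factors it gives 17.2–17.6, close to the rate-based 17.4–17.6 and well below 0.9 × (21.8 to 22.1) = 19.6–19.9.

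Nor can a reader conclude that the rule systematically favours VM202, since the sign changes with the assumed rates and baselines.

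The primary analyses use no imputation, and responder MOTH is one of three imputation analyses for this endpoint. The blinded regrouping step would also make empty cells rarer than in step 6. These points limit the importance of the concern but do not remove it. Neither of the other two imputations assumes that missing subjects behave like the other arm, and the logistic one lists neither treatment nor baseline pain among its covariates.

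**Conclusion.** The point holds in limited form. Cutting an imputed mean loses the other arm's response rate, and at the SAP's planning and Phase II rates fewer imputed subjects respond than in the donor arm. Because both arms are understated, the error in the responder difference is modest: up to about 1–2 points at 10% missing. At 20% it is about 2 points with five-factor matching, and larger (limit 3.4 at planning rates) only if almost no imputed subject responds. The direction is not fixed.

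The sizes rest on assumed baseline pain, missingness completely at random and evenly split matching factors. The mechanism does not rest on these assumptions.

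The documents do not support any doubt about the primary analyses, the type I error or the continuous MOTH result on this ground. This is a low-priority repair to a sensitivity analysis.

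**What to change.** Keep the principle for the responder version, but impute by draws from the other arm. Either of these would do:

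- Impute each missing Month 3, 6 and 9 score ten or more times from a model fitted in the other arm on baseline pain, gabapentin/pregabalin use, HbA1c, gender and age. Derive response within each draw, fit the categorical model, and pool the visit-specific differences.
- Draw the 0/1 outcome at the other arm's response rate given the same factors, again ten or more times, and pool.

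The first option makes the factor-removal rule unnecessary for this analysis. The second does so too if the rate comes from a model rather than from cells. If neither is adopted, the SAP should at least state that responder MOTH dichotomises an imputed mean, and should fix the order of factor removal before unblinding.

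The cost is a short SAP edit, one imputation step and slightly more programming. No data collection, sample size or primary analysis changes.
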